The population included in this study are pregnant Syrian refugee women between the ages of 18 to 49, who are in their first trimester of pregnancy.

6. 3. 1. Eligibility

Inclusion Criteria:

- Having the status of “Syrian under temporary protection”
- Being in the first trimester of the pregnancy
- Initial prenatal visit
- Age equal or greater than 18 years and less than or equal to 49

Exclusion Criteria:

- Having a citizenship or a status other than “Syrian under temporary protection”
- Not owning a mobile phone
- Being unable to read and write
- Not initial prenatal visit
- Having a chronic disorder or high-risk pregnancy that requires the individual to go to the hospital frequently. Frequently is defined as more than 3 visits post the baseline visit.
- While gestating, those that develop a high-risk pregnancy that requires more than 3 visits post the baseline visit.

6. 4. Sample Size Determination

The primary outcome measure for the power and size calculation is the difference in the mean number of visits among the different arms of the study. We set our target detectable difference in means to be 0.5 or more additional visits. As the maximum standard deviation is 1.5 due to the restricted range of 0 to 3 visits, our target effect size is $0.5/1.5 = 0.33$. Our calculation shows that each arm will need at least 40 patients to have a power of 90% and a two tailed significance level of 0.05. Due to the nature of refugees, we anticipate a high loss due to follow up and other reasons for dropout. Without prior information, we assume a 20% loss rate and therefore inflate the number of patients per arm by 25%. Thus, we plan to enroll 54 patients per arm for a total of 162 individuals. The statistical software G*Power Version 3.1.9.6 available from the UCLA Institute for Digital Research & Education Statistical Consulting website; [G*Power \(ucla.edu\)](http://G*Power (ucla.edu)), was used for the calculations.

6. 5. Randomization Strategy

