8.1. Primary Analysis

The primary analysis will be a standard one-way fixed effect ANOVA comparing the 3 arms. The resulting ANOVA results and the arm means with 95% confidence intervals will be presented.

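### The sample size treats a two-group standardised difference (0.5/1.5 = 0.33) as the ANOVA effect size f; under the plan's own inputs, power for 0.5 visits is about 31%, not 90%

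*Combined protocol and SAP*

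**What the plan says.** SAP section 6.4 bases the calculation on differences in mean visits between arms: "We set our target detectable difference in means to be 0.5 or more additional visits". It takes the SD from the limits of the scale ("As the maximum standard deviation is 1.5 due to the restricted range of 0 to 3 visits") and concludes that "our target effect size is $0.5/1.5 = 0.33". From this it reports that "each arm will need at least 40 patients to have a power of 90" per cent at a "two tailed significance level of 0.05", computed in G*Power. The G*Power test is not named, and the text does not say whether 0.33 is d or f.

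For dropout, "we assume a 20% loss rate and therefore inflate the number of patients per arm by 25" per cent, and "we plan to enroll 54 patients per arm for a total of 162 individuals".

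Section 8.1 fixes the test: "The primary analysis will be a standard one-way fixed effect ANOVA comparing the 3 arms". Section 5.3 frames the alternative as an increase in the intervention group relative to the control groups.

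**The concern.** A difference between two means divided by the SD is Cohen's d. One-way ANOVA power uses Cohen's f, the standard deviation of the arm means divided by the within-arm SD. For three equal arms whose means span a given range, f is at most sqrt(2)/3 = 0.47 of d. Entering d where f is expected therefore at least doubles the assumed effect and cuts the required sample size more than fourfold.

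The 90% figure is the only justification given for enrolling 162 women. If it is wrong, a non-significant result would be read as evidence that reminders do not add half a visit, when the trial had only about a one-in-three chance of detecting that effect under its own assumptions.

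**Working it through.** **Inputs** (section 6.4 unless noted): difference 0.5 visits; SD 1.5; two-sided alpha 0.05; 40 evaluable per arm; 54 enrolled per arm; 20% loss, so 54 × 0.8 = 43.2, about 43 evaluable. The test is a three-arm one-way ANOVA (section 8.1). The documents do not state any gap between the two control arms, so equal control means are assumed first and evenly spaced means second.

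**Formula.** With k = 3 arms of n and N = 3n, power = P(F′ > F crit). F′ is noncentral F with 2 and N − 3 degrees of freedom and noncentrality λ = N f².

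**Reproducing the plan's figure.** Take f = 0.33.
- n = 40: λ = 120 × 0.33² = 13.07, power 90.2%.
- n = 39: power 89.4%.

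The smallest n reaching 90% is therefore 40, exactly as stated. Reading 0.33 as d does not give 40: a two-sided two-sample t-test needs 191 per arm, a one-sided normal approximation 155, and even a one-sample t-test 97.

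**The f implied by 0.5 visits and SD 1.5.**
- One arm differs (means 0.5, 0, 0 above a common baseline). The grand mean is 1/6, so the deviations are 1/3, −1/6, −1/6. The SD of the means is sqrt[(1/9 + 1/36 + 1/36)/3] = 0.2357, and f = 0.2357/1.5 = 0.157. This equals (0.5/1.5) × sqrt(2)/3 and is the largest f possible for a 0.5-visit span.
- Evenly spaced means (0.5, 0.25, 0): SD of the means = sqrt[(0.0625 + 0 + 0.0625)/3] = 0.2041, and f = 0.136.

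**Power at SD 1.5.**

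| Evaluable per arm | λ = 3n × 0.157² | ANOVA, one arm differs | ANOVA, evenly spaced | Two-arm t-test |
|---|---|---|---|---|
| 40 | 2.96 | 31% | 24% | 31% |
| 43 | 3.19 | 33% | 26% | 33% |
| 54 (no loss) | 4.00 | 41% | 32% | 40% |

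**Sample size for 90% at SD 1.5.** The ANOVA with one arm differing needs 172 per arm, or 172/0.8 = 215 enrolled. A two-arm t-test needs 191 per arm, or 191/0.8 = 239 enrolled.

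**Difference detectable with 90% power at SD 1.5.** ANOVA: 1.05 visits at 40 per arm and 1.01 at 43. Two-arm t-test at 40 per arm: 1.10. These are about twice the target, on an outcome limited to 0 to 3.

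**Sensitivity to the SD** (difference 0.5, ANOVA, one arm differs):

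| SD | 40 per arm | 43 per arm |
|---|---|---|
| 1.5 | 31% | 33% |
| 1.2 | 46% | 49% |
| 1.0 | 62% | 66% |
| 0.8 | 82% | 85% |
| 0.7 | 91% | 93% |

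The largest SD giving 90% power for 0.5 visits is 0.72 at 40 per arm, 0.74 at 43 and 0.84 at 54.

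**The case against.** The strongest objection is that 1.5 is a ceiling, not an expectation. On a 0 to 3 scale the SD cannot exceed sqrt(m(3 − m)) at mean m. It reaches 1.5 only when half the women attend no visits and half attend all three, so arms whose means differ by 0.5 cannot all have it. With visits spread evenly over 0 to 3 (an illustrative assumption, SD 1.12), power at 43 per arm is 55%. With three independent visits each attended with probability one half (also illustrative, SD 0.87), it is 79%. This stands as a reason to call 31% conditional: the documents give no expected SD, so the power actually attained is unknown. It does not rescue the claim, because section 6.4 itself pairs SD 1.5 with 40 per arm and 90%, and neither illustration reaches 90%.

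Second, the use of d as f is inferred. Section 6.4 does not name the G*Power test, its two-tailed wording does not fit an F test, and unrounded f = 1/3 gives 39 rather than 40. That is fair, but the stated inputs fail to give 90% whatever was entered in the software.

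Third, 40 is not the planned enrolment. True, but 43 evaluable gives 33%, and 54 with no loss gives 41%.

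Fourth, section 5.3 points towards intervention against controls, and pooling the controls raises power to 40% (40 versus 80) or 43% (43 versus 86). Section 8.1 does not specify that contrast, and it too falls well short of 90%.

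**Conclusion.** The concern holds. With 0.5 visits, SD 1.5, alpha 0.05 and 40 evaluable per arm, the planned ANOVA has 31% power rather than 90%, assuming equal control means, which is the most favourable pattern. It has 24% if the three means are evenly spaced. At the planned enrolment less 20% loss it is 33%. The exact match at f = 0.33 makes the substitution of d for f the very likely cause, but the conclusion does not rest on that inference. It does depend on the SD: a smaller SD would raise power, but 90% at 40 per arm requires about 0.72 or less, under half the stated value and without support in the documents.

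**What to change.** Correct SAP section 6.4 and keep enrolment at 162:

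1. Delete the claim that 40 per arm gives 90% power for 0.5 visits. Name the test and define the effect size as f, showing its derivation from the assumed arm means.
2. State that 54 enrolled per arm, about 43 evaluable after 20% loss, gives about 33% power for 0.5 visits at SD 1.5 and about 90% power for a difference of about 1.0 visit.
3. Add power for 0.5 visits by SD at 43 per arm: 33% (SD 1.5), 49% (1.2), 66% (1.0), 85% (0.8).
4. Commit to interpreting a non-significant result through the 95% confidence interval of the between-arm difference. Section 8.1 currently promises intervals only for the arm means, so it must name the comparison and add this output.
5. While editing, reconcile the inflation step: 40 × 1.25 = 50, not 54. The planned 54 fits a base of 43 (43/0.8 = 53.75).

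The cost is SAP wording plus one extra output, with no additional patients. The stated power becomes less favourable. Section 6.5 already allows further recruitment after a sample-size check, but restoring 90% for 0.5 visits at SD 1.5 would need about 215 enrolled per arm (3 × 215 = 645 in all). That would be a separate design decision for the sponsor, and this correction does not depend on it.

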Alternative hypothesis: Sending reminders on participants' upcoming appointments 2 weeks before, 1 day before, and on the day of the appointment will result in a percent increase on the number of appointments that are attended by the intervention group compared to the control groups.

6. Study Methods

6. 1. Study Type

This is a behavioral intervention study using an unblinded, parallel groups, randomized controlled study design. The intervention group ("Reminder") will download and use the HERA application to receive appointment reminders through push notifications. The control group ("No reminder") will not be using the HERA application, and therefore won't be provided with any reminders. The third group will also be a non-notified control group, i.e., "No reminder" as well.

The third group's data will be collected retrospectively via hospital records. The intent of the 3rd arm is to estimate the “true” baseline for the number of visits without any extra attention given by the medical staff, in order to prevent inadvertent behavior modification through perceived observation bias.

6. 2. Study Procedure

Pregnant Syrian refugee women who are in their first trimester of pregnancy will be enrolled in the study. Participants will be enrolled from the Obstetrics and Gynecology department of refugee health clinics in Istanbul. Participants will be randomized and enrolled into intervention or either of the two control arms (refer to section 6.5. Randomization Strategy for details).

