For the intervention arm, participants will be given the consent form. After having consented to participate in the study, they will be given the socioeconomic and health history form. In what follows, they will receive a 30-minutes brief about the mobile app HERA and will be asked to download it. The mobile application will automatically plan out the dates of further prenatal care appointments based on the date of the last menstruation. Participants will receive reminders in the form of push notifications for prenatal checkup dates for 6 months. Reminders will be sent at the following intervals: 1) 2 weeks before, 2) 1 day before and 3) on the day of the recommended appointment. After the recommended appointment date, participants will receive push notifications asking whether or not they went to the appointment in weekly intervals for 1 month. This reminder algorithm will be used for each prenatal checkup for a total of three appointments post the baseline visit: once in second trimester and two in third trimester, using the World Health Organization and Turkish Ministry of Health prenatal checkup calendar. At the end of 6 months of follow up time, participants in the intervention arm will be contacted via phone call to ask for any remaining appointments or unanswered notifications. Completeness of 3 prenatal care appointments post the baseline visit, as recommended by WHO and implemented by Turkish MoH will be compared to the control groups.

Participants in the informed control arm will be given the consent form and will be asked for their contact information if consented. They will also be given the socioeconomic and health history form. Participants in the non-informed control group just will be given the socioeconomic and health history form. Both the informed and non-informed control group members will be

reached out at the end of the 6-month study period to be asked about the number of prenatal care appointments they attended. If unable to be reached, retrospective chart review of the participant's medical record will be attempted, in order to obtain the number of attended prenatal care appointments.

6. 2. 1. Recruitment Strategy

Participants will be enrolled from the obstetrics and gynecology department of refugee health clinics in Istanbul, Turkey with the help of a translator (Turkish to Arabic). The enrollment will take place with the help of the physician.

6. 3. Study Population

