Subjects will be selected on the following basis: randomly select a week and recruit on 6 days of that week. On 3 of the days the selection process will start in the morning, denoted as AM, (the first part of the day that is expected to see half of the patients) and on the other 3 days the selection process will start in the afternoon, denoted as PM, (the second part of the day that is expected to see half of the patients.) For each AM/PM session, the first 27 subjects giving approval to be in the study will be randomly assigned into one of the 3 arms. It is estimated that 100 to 200 women use the hospital daily. Thus, we feel that most likely the daily target intakes will be met. However, if not met by the end of the AM/PM shift, the selection process will stop. After day 6 and before any data analysis, a check will be done on the sample sizes and additional subjects may be recruited by selecting another week to perform additional recruiting.

This sampling plan requires that the number of women coming to see the medical staff be approximately the same day to day and AM to PM.

Details of the random assignment to AM/PM and to groups are attached. The assignment of treatment and control groups to 0, 1 or 2 will be done prior to the start of subject recruitment but will not be shared with the data analyst until after the analysis is complete.

7. Outcomes

Primary Outcome:

The primary outcome of this study is the number of medical visits, following the initial baseline PNC visit, over the 6-month period prior to childbirth.

Secondary analyses:

In the secondary analyses, we will further examine other risk factors, including sociodemographic and reproductive medical history, on the number of medical visits during the study period. The following additional data will be gathered:

1. Age
2. Highest level of education
3. Current employment status and profession if employed
4. Marital status
5. If married, whether the spouse is alive or deceased
6. If married, whether the spouse resides with the participant or not
7. Number of children
8. Ages of children
9. Miscarriage history, and the number and the timing of miscarriage, if any
10. Number of deceased children, if any
11. Number of times the participant gave birth to stillborn baby, if any
12. If prior pregnancies, the number of deliveries occurred at home and at a hospital
13. Type of delivery (vaginal, C-section) and the number of each type

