7.1. Populations and subgroups to be analyzed Per Protocol (PP)

All randomized study subjects not rejected over the observation period and having complete data will be the basis of the analysis. Subjects with missing data will be excluded from the analysis. This will be the primary population for the analysis.

8. Analysis

All outcomes will be presented using descriptive statistics, continuous data by the mean, standard deviation and a plot of the pdf. Binary and categorical variables will be presented in tables using counts. R version 4.0.5 will be used for all statistical analysis.

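### SAP 6.5 puts approval before assignment, but the arm-specific consent form in SAP 6.2 implies a refusal step after assignment in two arms only, so the sections must be reconciled and refusers accounted for

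*Combined protocol and SAP*

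**What the plan says.** **Order in SAP 6.5 (Randomization Strategy).** In each session, "the first 27 subjects giving approval to be in the study will be randomly assigned" to one of three arms. Approval comes first, and it covers all three arms.

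**Order in SAP 6.2 (Study Procedure).** The section opens with "Participants will be randomized and enrolled into intervention or either of the two control arms" and refers to 6.5 for details. It then describes consent arm by arm:

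- Reminder: "For the intervention arm, participants will be given the consent form". The history form follows consent, and after that "they will receive a 30-minutes brief about the mobile app HERA and will be asked to download it".
- Informed control: "Participants in the informed control arm will be given the consent form and will be asked for their contact information if consented". These women also get the history form.
- Non-informed control: "Participants in the non-informed control group just will be given the socioeconomic and health history form".

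**Masking.** The Study Protocol (Study Design) declares the trial open label.

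**Analysis population in SAP 7.1.** "All randomized study subjects not rejected over the observation period and having complete data will be the basis of the analysis". Women with missing data are left out. The primary analysis in SAP 8.1 is a one-way ANOVA of the three arms, with no covariates named.

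**Missing data in SAP 8.3.** Phone calls and hospital-record review are planned for women with missing data. No section says how a woman who refuses the consent form after assignment is counted or analysed.

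**The concern.** A form handed to two arms and withheld from the third can be given out only when the arm is known. Read that way, 6.2 has a point after assignment at which women in the reminder and informed control arms may refuse, and women in the non-informed arm may not. If refusers are then absent from the analysis, two arms consist of willing women and the third of everyone assigned to it.

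Women who refuse a study of prenatal attendance may well attend less. Losing them would raise the mean in the consenting arms even if reminders did nothing, and an ANOVA without covariates would not adjust for that. The third arm is meant to supply the undisturbed baseline (SAP 6.1), so the comparison most exposed is one that the design was built to provide.

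**Working it through.** **Step 1. Can the two sections be followed together?**

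| | SAP 6.5 | SAP 6.2 |
|---|---|---|
| Reminder | approval, then assignment | consent form, history form, briefing and download |
| Informed control | approval, then assignment | consent form, contact details if she consents, history form |
| Non-informed control | approval, then assignment | history form only |

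If the approval in 6.5 is the consent form in 6.2, the sections conflict, because the non-informed arm has the first and not the second. If they are two separate steps, the wording can be made to agree, but a refusal step remains after assignment in two arms and not in the third.

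**Step 2. Would a refuser leave the analysis?** In the reminder arm the history form comes after consent, so a refuser would have no form. The chart-review fallback in 6.2 is written for the two control groups. SAP 8.3 offers record review more generally but does not mention refusers. Exclusion under 7.1 is therefore probable, though not stated.

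**Step 3. Size against an arm with no refusals.** Let q be the share refusing after assignment, and D the number of visits by which refusers fall short of consenters. If consenters average m, everyone assigned averages (1 − q)m + q(m − D) = m − qD. Analysing consenters only gives m, so the bias is qD. The documents give neither q nor D, and both are assumed here. The target difference of 0.5 visits is from SAP 6.4.

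| q | D (visits) | Bias qD (visits) | Share of 0.5 target |
|---|---|---|---|
| 0 | any | 0 | 0% |
| any | 0 | 0 | 0% |
| 10% | 0.5 | 0.05 | 10% |
| 20% | 1.0 | 0.20 | 40% |
| 30% | 1.0 | 0.30 | 60% |

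**Step 4. Reminder against informed control.** Both arms have a refusal step, so the bias is the difference between their two qD values. It is zero if refusal is alike in both. With D = 1.0 in both, and 20% refusing in one and 10% in the other, it is 0.20 − 0.10 = 0.10 visits (assumed).

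**Step 5. Effect on the primary test.** The planned intake is 6 sessions × 27 = 162, or 54 per arm, as SAP 6.4 states. After the assumed 20% loss, 54 × 0.8 = 43.2, taken as 43 per arm and held equal for simplicity. Suppose reminders have no effect and selection shifts one arm's mean by b. The noncentrality of the F test is 43 × (2/3)b²/SD², with 2 and 126 degrees of freedom. The SD of 1.5 is the plan's maximum, and 1.0 is an assumption.

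| b (visits) | Rejection rate, SD 1.5 | Rejection rate, SD 1.0 |
|---|---|---|
| 0 | 5% | 5% |
| 0.05 | 5.2% | 5.5% |
| 0.20 | 8.9% | 14.3% |
| 0.30 | 14.3% | 27.5% |

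The rates are the same if both consenting arms shift by b and the non-informed arm does not.

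**The case against.** The best defence is that 6.2 never says in one sentence that consent follows assignment. It refers to 6.5, which puts approval first, and its arm-by-arm paragraphs can be read as a list of what each group receives and not as a timeline. SAP 6.5 also mentions an attachment on random assignment. That attachment and the consent form were not in the text examined, and either might describe a common approval step. This stands as far as order is concerned: the sequence in 6.2 is an inference. It does not settle the matter, because the consent form still differs by arm and the treatment of refusers is still unstated.

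Three stronger readings are tempting, and the documents do not support them.

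- A reader might infer that women who turn down the briefing or the download are dropped. SAP 6.2 places both after consent, and 7.1 has no adherence criterion despite its per-protocol heading. Such a woman can be phoned at 6 months or traced through records and can stay in her arm. Only refusal of the consent form is at issue.
- A reader might infer that only the reminder arm is self-selected. The informed control arm receives a consent form too.
- A reader might take the 10% to 60% in the table as an estimate. It is arithmetic on assumed inputs, it applies only against an arm with no refusals, and the range includes zero.

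It is also fair to say that an identical, fully informative approval could undercut the purpose of the non-informed arm. That limits the fix but leaves the problem in place.

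**Conclusion.** The point holds as an unreconciled procedure with a plausible route to bias. SAP 6.5 and 6.2 do not fit together on when and from whom agreement is sought. On the most charitable reading, two arms still have a refusal step after open-label assignment and the third has none, and the population in 7.1 would probably turn refusals into exclusions.

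The clearest bias is in reminder, or informed control, against non-informed control. Reminder against informed control is biased only if refusal differs between those two arms. The upward direction assumes that refusers attend less, which is plausible but not shown. The documents do not allow the size to be estimated. The assumed cases run from 0 to 0.30 visits, and other inputs would give other values. The plan should be corrected on this point, but it does not follow that the results would be biased: if nobody refuses, or refusers attend as often as others, nothing is lost.

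**What to change.** 1. Amend SAP 6.2 so that the approval described in 6.5 is completed in all three arms before the assignment is opened. The app briefing and the contact-detail step then follow assignment.
2. Amend SAP 7.1 so that every assigned woman stays in her assigned arm for the primary analysis. Where her approval allows, take her visits from the hospital-record review already planned in 8.3.
3. Report the numbers assigned, refusing and analysed, by arm.
4. What the approval tells women in the non-informed arm is for the ethics board. If consent must follow assignment in some arms, say so, apply the same counting rule, and state that comparisons with the non-informed arm may be affected by selection.

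**Cost.** Wording changes in 6.2 and 7.1, a possible notification to the ethics board, and some extra record review. No extra patients are needed.
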